Official Title: EngagINg the COmmunity to Reduce Preterm Birth Via  
Adherence To an Individualized Prematurity Prevention Plan  
(INCORPorATe IP3)

NCT: NCT04933812

IRB Document Date: 01/17/2023

Previous studies have shown preterm births (PTB) are high in non-Hispanic Black (NHB) women and women are more likely to have a PTB if they previously had one. Pregnant women with history of PTB at Duke Maternal Fetal Medicine receive IP3 plans to reduce the risk of recurrent PTB and these interventions are often stressful. The EnagagINg the Community to Reduce Preterm Birth via Adherence To an Individualized Prematuritiy Prevention Plan (INCORPorATe IP3) was developed to provide support for NHB women who had prior PTB. This intervention included information provided through Facebook group discussions with doulas and Zoom group meetings to review a variety of pregnancy-related topics.

Participants received questionnaires to complete at intake, between 20-28 weeks GA, and after 30 weeks GA in addition to group satisfaction surveys after each Zoom meeting. Results from the questionnaires and surveys will be reported as counts (percentages) for categorical variables and mean (SD), median (IQR), and range for continuous variables.

Table 1. Participant Characteristics	
Characteristic	
Age (mean, SD)	
Number of Prior Preterm Births (median, IQR)	
Insurance Status	
Public	
Private	
None	
Body mass index at prenatal care intake (mean, SD)	
Chronic hypertension	
Pre-gestational Diabetes	
Tobacco use at any time in pregnancy	
Preterm Birth Preventative Recommendations (i.e., IP3 plan)	
Lifestyle modifications (n, %)	
Cervix length/Cerclage (n, %)	
Progesterone (n, %)	
Low Dose Aspirin (n, %)	
All data are reported as n (%) unless detailed otherwise	

Table 2. Feasibility and Acceptability Measures	
Recruitment: #Eligible people approach/ # recruited	
Facebook Engagement: Number of participants who logged onto the Facebook page Number of participants who posted/reposted anything Facebook engagement metrics	
Group Social Support (GSS) Session Engagement: Median number of GSS visits attended [IQR] Number (%) of participants who attending 5 or more sessions	

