The primary objective of this protocol is to determine if INCORPorATe IP3 is feasible prior to a larger trial focused on determining efficacy. Feasibility will be measured using the RE-AIM framework⁴: *Reach or Participation (Primary Outcome)*: (a) percent of eligible participants who are successfully recruited and attend at least one group session; *Effectiveness*: retention rate in the intervention; *Implementation*: fidelity to the intervention protocol; *Maintenance*: intervention sustainability based on continued engagement from the participants.

Methods:

Recruitment:

We plan to pilot our intervention with three groups of 5 – 20 women (total up to 60 women). We plan to enroll women who are currently pregnant up to 20 weeks of gestation, who self-identify as non-Hispanic black with a history of prior preterm delivery (before 37 weeks gestation) due to idiopathic preterm labor, preterm pre-labor rupture of membranes, cervical insufficiency or preeclampsia. Further we will include women who are receiving care with the Duke Perinatal Clinics and plan to deliver within

the Duke Health System. We will exclude non-English speaking women, multiple gestation and women with current or prior pregnancy with major fetal anomaly. We will identify participants meeting the eligibility criteria via review of potential participant's electronic medical record. Eligible participants will be approached for enrollment.

Intervention Delivery:

Given limitations of in-person gatherings in light of the COVID 19 pandemic, we developed the intervention to be delivered via virtual platforms. The study protocol will be an adjunct rather than a replacement of traditional prenatal care with Duke Perinatal. The core components of the intervention will be interaction with community doulas and other NHB with prior PTB via facebook group page and group meetings.

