We will recruit 60 pregnant women from the Duke Perinatal Clinics with the following inclusion criteria: self describe race NHB, history of prior singleton preterm delivery (before 37 weeks gestation, current singleton gestation, with IP3 plan. We will exclude women with anomalous fetuses, age below 18 or are non-English speaking. The study staff will approach the subject and provide information regarding the study. If the patient is interested in participating, then study staff will obtain informed consent at that time. The patient can take as much time to decide about participation and the study team will come up with a plan with the patient to follow up on a decision to participate. Voluntariness will be emphasized. Patients will also be told that they were identified as being eligible because their medical chart indicated they have a history of a prior spontaneous preterm birth. For those patients who choose to 'opt out,' to

prevent unwelcome emails, phone calls, or other contacts from those other than a patient's clinician, researchers/study teams must check the opt out status for each patient who may be eligible for their study and exclude those not wishing to be contacted.

Subject Recruitment and Compensation Describe recruitment procedures, including who will introduce the study to potential subjects. Describe how you will ensure that subject selection is equitable and all relevant demographic groups have access to study participation (per 45 CFR 46.111(a) (3)). Include information about approximately how many DUHS subjects will be recruited. If subjects are to be compensated, provide specific prorated amounts to be provided for expenses such as travel and/or lost wages, and/or for inducement to participate.

We will screen clinic schedules and approach women meeting the eligibility criteria during a clinic visit. Consenting participants will be compensated \$20 at intake and \$20 after completion of the exit interview.

There will be three meetings in total.
\$20 for each participant for coming to the meeting and then a raffle of \$200 (which one person will win).
This will happen at all three meetings.

Then there is another 'spot prize' of \$200 which will be raffled for all those that attended the interview – again 1 winner.

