**Table 3. Group Social Support Sessions**

Session #	Topics Covered	# Attended/# Enrolled at session timepoint	Post-meeting survey % very satisfied % somewhat satisfied %non satisfied	No-Show Survey Results
#1				
Date				
#2				
Date				
#3				
Date				
#4				
Date				
#5				
Date				
#6				
Date				

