**Table 4. Other Feasibility and Acceptability Measures**

Recruitment: #eligible people approach/ # recruited	
Retention: # participants who completed all survey measures Avg # survey measures completed/participant	
Facebook Engagement: Number of participants who logged onto the Facebook page Number of participants who posted/reposted anything Facebook engagement metrics	
Healthcare Utilization	

Table 5. Adherence and Pregnancy Outcomes	
Preterm Birth Preventative Recommendation Adherence (adhered/recommended, percent)	
Lifestyle Modifications	
IOM weight gain guidelines	
Tobacco cessation	
Supplemental Progesterone	
17-P	
Vaginal progesterone	
Cerclage/Serial Cervix Length	
Cerclage	
Serial cervix lengths	
Low Dose Aspirin	
Pregnancy Outcomes (n, %)	
Preterm Birth/Gestational Age Outcomes:	
Preterm delivery <37 weeks	
Gestational age at delivery in weeks, mean (SD)	
Length of gestation in current pregnancy compared to earliest preterm birth, mean (SD)	
Maternal Outcomes:	
Preeclampsia/gestational hypertension	
Number of antepartum triage evaluations, median (IQR)	
Antepartum hospital admission	
Length of delivery admission in days, median (IQR)	
Neonatal Outcomes:	
Birth weight in grams, mean (SD)	
Neonatal Intensive care unit admission	

Table 6. Secondary Quantitative Measure (mean, SD)	Intake N= 32	Protocol Completion N=	Change
Interpersonal Process of Care (IPC-18) at protocol completion			
Description: Validated 18-question instrument that measures patient care experience during clinical visits in four domains. Scores for each domain range from 1 to 5 on a Likert scale			
Communication Domain			
Lack of clarity (higher scores are negative, denote increased lack of clarity from clinicians)			
Elicits concern (higher scores are positive, denotes the clinician elicited concerns more often)			
Explain results (higher scores are positive, denotes the clinician explained results more often)			
Decision Making Domain			
Decision Making (higher scores are positive, denoting more collaborative decision making between the clinician and patient)			
Interpersonal Style Domain			
Emotional support (higher scores are positive, denoting more emotional support from the clinician)			
Discrimination due to race/ethnicity (higher scores are negative, denote increased discrimination from clinicians)			

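### The SAP has no row for the protocol's primary outcome (Reach), and its planned recruitment and attendance outputs do not determine it

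*SAP*

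**What the plan says.** The protocol's primary objective (end of the Introduction) is feasibility ahead of a larger efficacy trial. It marks a single measure as primary, Reach, defined as the "percent of eligible participants who are successfully recruited and attend at least one group session". A woman counts only if she is recruited and also attends, and the base is eligible women.

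The SAP does not use the word Reach and designates no primary outcome. Its relevant outputs are:

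- Table 2, Recruitment: "Recruitment: #Eligible people approach/ # recruited". Table 4 repeats it: "Recruitment: #eligible people approach/ # recruited".
- Table 2, session engagement: "Median number of GSS visits attended [IQR] Number (%) of participants who attending 5 or more sessions".
- Table 3, for each of six sessions: "Attended/# Enrolled at session timepoint".
- Table 4, Retention: completion of survey measures, not attendance.

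On the denominator, the protocol's Recruitment section says "Eligible participants will be approached for enrollment". Its Selection of Subjects section requires study teams to "check the opt out status for each patient who may be eligible for their study and exclude those not wishing to be contacted".

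**The concern.** A SAP should at least say how the primary outcome is calculated. Here the row closest to it stops at recruitment, so a woman who consents and never joins a session counts as a success. The attendance rows use a different threshold (5 or more), a median, or separate session totals. None gives the number of women who came at least once.

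Reach is the primary measure for the trial's stated purpose, judging feasibility before a larger study. If the tables are filled in as drawn, readers will have a recruitment figure but not the primary outcome. The recruitment figure can only equal or exceed Reach when all eligible women are approached.

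**Working it through.** The documents give no value, target or interval for Reach, so there is no figure to reproduce. The check has three parts.

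**1. Can Reach be deduced from the planned outputs?**

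Inputs: six sessions (SAP Table 3) and 32 women. The 32 is an assumption: SAP Table 6 prints it only as the intake column's N for the questionnaires. Also assumed: all 32 are enrolled at every session, and 13 attend each session, so total attendances are 6 × 13 = 78.

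Two patterns, as number of women by sessions attended:

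| Sessions attended | 0 | 1 | 2 | 3 | 4 | 5 | 6 |
|---|---|---|---|---|---|---|---|
| Pattern A | 7 | 2 | 9 | 5 | 3 | 5 | 1 |
| Pattern B | 1 | 9 | 13 | 0 | 3 | 5 | 1 |

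- Women: 32 in each.
- Attendances: A = 2 + 18 + 15 + 12 + 25 + 6 = 78; B = 9 + 26 + 0 + 12 + 25 + 6 = 78.
- Median (16th and 17th ordered values): 2 in both. Lower quartile (8th and 9th): 1 in both. Upper quartile (24th and 25th): 4 in both.
- 5 or more sessions: 5 + 1 = 6 women in both.
- Range 0 to 6 and mean 78/32 = 2.44 in both.
- Attendance per session: assign sessions in rotation, each woman taking the next ones in turn. No woman takes more than six, so none repeats a session, and 78 attendances over six sessions give 13 at every session in both.

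Women attending at least once: A = 32 − 7 = **25**; B = 32 − 1 = **31**. Enumerating all distributions with these same outputs gives every count from 25 to 31. The planned outputs bound the count but do not fix it.

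**2. How far can the recruitment percentage sit from Reach?**

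If every eligible woman is approached,

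Reach = (recruited / approached) × (attended at least once / recruited).

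The relative gap therefore depends only on the share of recruits who ever attend. With 32 recruited and an assumed number of eligible women, all approached:

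| Eligible | Recruited/approached | Reach, pattern A | Reach, pattern B |
|---|---|---|---|
| 40 | 32/40 = 80.0% | 25/40 = 62.5% | 31/40 = 77.5% |
| 60 | 32/60 = 53.3% | 25/60 = 41.7% | 31/60 = 51.7% |
| 80 | 32/80 = 40.0% | 25/80 = 31.3% | 31/80 = 38.8% |

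For scale, the Wilson 95% intervals with 80 eligible are 22.2–42.1% for 25/80 and 30.0–51.0% for 32/80. Read as a ratio, the printed row would give 80/32 = 2.5 rather than 40.0%.

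**3. Is the denominator defined?**

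Not fully. If all eligible women are approached, eligible and approached coincide. Women who have opted out of contact cannot be approached, and the SAP does not say whether they count as eligible. For illustration, if 80 women are eligible and 20 have opted out, leaving 60 approached, pattern B gives 31/80 = 38.8% or 31/60 = 51.7%.

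The protocol's two eligibility lists also differ. The gestational-age limit ("We plan to enroll women who are currently pregnant up to 20 weeks of gestation") is only in Recruitment. The requirement for an IP3 plan and the exclusion of women under 18 are only in Selection of Subjects.

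**The case against.** This is a descriptive feasibility pilot. No test, target or progression threshold is attached to Reach, so no formal decision reverses. The protocol (Outcome Measures) plans to monitor meeting attendance, and the Table 2 median and 5-or-more count need it for each participant, so anyone holding the data can compute the numerator. The SAP never presents Recruitment as Reach, and the slash may only separate two counts. The SAP is dated 01/17/2023, nearly two years after the protocol, so an intervening change of outcomes is conceivable.

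Much of this stands as fact. It makes the repair easy and means the inverted ratio may be a labelling slip. It is also true that some results would fix the count, such as a session attended by every enrolled woman, but the plan does not ensure that. The SAP's sentence promising a range applies to questionnaires and surveys, and patterns A and B agree on range anyway.

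None of it places the primary outcome in the plan. A descriptive SAP still has to describe the primary outcome, and neither document shows that Reach was redefined or dropped. The differing eligibility lists are a separate protocol inconsistency; they matter here only because they leave the denominator open.

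**Conclusion.** The point holds: the SAP is wrong as written because it omits the sole primary outcome, and this must be corrected. That conclusion rests on the text alone and on no assumed number.

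The size of any misstatement cannot be known from the documents. Under the assumptions above (32 recruited, 80 eligible, all approached), identical planned outputs are compatible with Reach of 31.3% or 38.8%, against a recruitment figure of 40.0%. Each recruit who never attends lowers Reach by 1/80 = 1.25 percentage points. Recruitment equals Reach only if all eligible women are approached and every recruit attends at least once.

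**What to change.** - Add a row labelled as the primary outcome: number recruited who attended at least one group session / number eligible, as n/N (%). A 95% interval is preferable but optional.
- Write the Recruitment row in Tables 2 and 4 as recruited/approached, and show the flow from eligible to approached to recruited to attended at least once.
- Define 'eligible' by the criteria actually applied at screening, and state how opt-outs are counted. Reconcile the two protocol eligibility lists openly rather than merging them after enrolment.
- If no count of eligible but unapproached women was kept, say so and report the denominator as eligible women approached.

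The cost is one row and a corrected label, with no change to trial conduct or to attendance data collection. Neither document says that eligible but unapproached women were logged, so the full denominator may be lost. The reported percentage may also be lower than the recruitment figure.

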**Table 3. Group Social Support Sessions**

Session #	Topics Covered	# Attended/# Enrolled at session timepoint	Post-meeting survey % very satisfied % somewhat satisfied %non satisfied	No-Show Survey Results
#1				
Date				
#2				
Date				
#3				
Date				
#4				
Date				
#5				
Date				
#6				
Date				

**Table 4. Other Feasibility and Acceptability Measures**

Recruitment: #eligible people approach/ # recruited	
Retention: # participants who completed all survey measures Avg # survey measures completed/participant	
Facebook Engagement: Number of participants who logged onto the Facebook page Number of participants who posted/reposted anything Facebook engagement metrics	
Healthcare Utilization	

Table 5. Adherence and Pregnancy Outcomes	
Preterm Birth Preventative Recommendation Adherence (adhered/recommended, percent)	
Lifestyle Modifications	
IOM weight gain guidelines	
Tobacco cessation	
Supplemental Progesterone	
17-P	
Vaginal progesterone	
Cerclage/Serial Cervix Length	
Cerclage	
Serial cervix lengths	
Low Dose Aspirin	
Pregnancy Outcomes (n, %)	
Preterm Birth/Gestational Age Outcomes:	
Preterm delivery <37 weeks	
Gestational age at delivery in weeks, mean (SD)	
Length of gestation in current pregnancy compared to earliest preterm birth, mean (SD)	
Maternal Outcomes:	
Preeclampsia/gestational hypertension	
Number of antepartum triage evaluations, median (IQR)	
Antepartum hospital admission	
Length of delivery admission in days, median (IQR)	
Neonatal Outcomes:	
Birth weight in grams, mean (SD)	
Neonatal Intensive care unit admission	

Table 6. Secondary Quantitative Measure (mean, SD)	Intake N= 32	Protocol Completion N=	Change
Interpersonal Process of Care (IPC-18) at protocol completion			
Description: Validated 18-question instrument that measures patient care experience during clinical visits in four domains. Scores for each domain range from 1 to 5 on a Likert scale			
Communication Domain			
Lack of clarity (higher scores are negative, denote increased lack of clarity from clinicians)			
Elicits concern (higher scores are positive, denotes the clinician elicited concerns more often)			
Explain results (higher scores are positive, denotes the clinician explained results more often)			
Decision Making Domain			
Decision Making (higher scores are positive, denoting more collaborative decision making between the clinician and patient)			
Interpersonal Style Domain			
Emotional support (higher scores are positive, denoting more emotional support from the clinician)			
Discrimination due to race/ethnicity (higher scores are negative, denote increased discrimination from clinicians)			
Disrespectful to office staff (higher scores are negative, denote increased disrespectful behavior from clinicians towards office staff)			
Maternal Social Support Scale (MSSS)			
Description: Six question questionnaire answered from 1 to 5 on a Likert scale, higher scores are positive and denote increased support			
MSS at intake			
MSS at protocol completion			
Pregnancy Specific Anxiety (PSA) at 28 weeks			
Description: Frequency of four emotions rated from 1 to 5 on a Likert scale, higher scores are negative and denote increased anxiety			
PSA at intake			
PSA at 3 rd trimester

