Official Title: EngagINg the COmmunity to Reduce Preterm Birth Via
Adherence To an Individualized Prematurity Prevention Plan
(INCORPorATe IP3)

NCT: NCT04933812

IRB Document Date: 03/01/2021

EngagINg the COmmunity to Reduce Preterm Birth via Adherence To an Individualized Prematurity Prevention Plan (INCORPorATe IP3): A feasibility study protocol

Introduction:

Non-Hispanic black women are 49% more likely to experience a preterm birth (PTB), delivery before 37 weeks. PTB is associated with increased risk of poor short and long-term neonatal outcomes. PTB can occur in multiple clinical scenarios including spontaneous PTB (e.g. preterm labor, preterm pre-labor rupture of membranes) and medically induced preterm labor (e.g. preeclampsia). Women with a history of PTB are at 1.5 – 2 fold increased risk for future PTB. There are medical therapies that can reduce the risk of recurrent PTB specific to the presumed etiology of the prior PTB. Thus, women with a history of a prior PTB who receive care with Duke Maternal Fetal Medicine (MFM) receive an Individualized Prematurity Prevention Plan (IP3) to reduce their risk of recurrent PTB. The IP3 plans are often labor intensive with requirements ranging from daily medications, weekly clinic visits, painful injections or invasive ultrasounds.

Given the increased rate so of PTB among NHB women and some suggestion of decreased adherence in this population¹, we previously conducted qualitative studies with NHB women to uncover patient perceived barriers to IP3 adherence^{2,3}. These studies revealed that NHB women with prior preterm birth felt that stress and lack of support were key barriers to preterm birth prevention adherence. Stress and limited support made women feel isolated from their peers and community. Based on these data we worked with a stakeholder group to develop a patient-centered, community-involved intervention that will increase adherence to an individualized prematurity prevention plan using community-level social supports. The resulting intervention titled, EngagINg the COmmunity to Reduce Preterm Birth via Adherence To an Individualized Prematurity Prevention Plan (INCORPorATe IP3) includes community doula led group social support.

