We will collect basic demographic and pregnancy information based on chart review. Baseline demographics will include age, medical comorbidities, and pregnancy history. During the intervention, we will monitor intervention engagement based on Facebook page engagement, attendance to group meetings and completion of surveys/measures. We will also collect measures of IP3 knowledge, perceived social support, pregnancy specific anxiety and maternal social support using validated scales at three timepoints: intake, after meeting #4, and after the final meeting (#8).

- **IP3 knowledge questionnaire** includes approximately four questions aimed to evaluate a participant's knowledge about the details of their IP3 plan. Participants will only receive questions that pertain to their specific IP3. They will be given the answers immediately following the assessment
- **Pregnancy-Specific Anxiety (PSA):** The PSA is a validated 13-item tool used to assess anxiety specific to pregnancy this tool has been correlated with preterm birth outcome.
- **Interpersonal Processes of Care (IPC):** The IPC is an 18-question questionnaire that asks participants about their experience with receiving care within a specific clinic (in this case the Duke Perinatal Durham Clinic).
- **Maternal Social Support Scale (MSSS):** The MSSS is a six-question scale that quantifies a pregnant woman's social support as low, medium or adequate.
- **IP3 Adherence Data:** We will gather data on adherence to the IP3 based on both participant report and EHR chart review.

We will review the medical record to determine adherence to the IP3 plan and record delivery outcomes (e.g. gestational age at delivery, delivery route, length of hospital stay, etc.)

Selection of Subjects List inclusion/exclusion criteria and how subjects will be identified:

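### Does the SAP Table 5 comparison of current gestation with the earliest prior preterm birth need a definition and a caution in the plan?

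*SAP*

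**What the plan says.** SAP Table 5 (Adherence and Pregnancy Outcomes) lists, among the gestational-age outcomes, "Length of gestation in current pregnancy compared to earliest preterm birth, mean (SD"). It gives no unit, direction, definition of *earliest* or footnote. The row just above it, gestational age at delivery, is in weeks.

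The comparator is set by eligibility. The protocol's Recruitment section takes women "with a history of prior preterm delivery (before 37 weeks gestation") "due to idiopathic preterm labor, preterm pre-labor rupture of membranes, cervical insufficiency or preeclampsia". Its Selection of Subjects section asks for "history of prior singleton preterm delivery (before 37 weeks gestation, current singleton gestation, with IP3 plan". Enrolment is open up to 20 weeks, so the length of the current pregnancy is not restricted at 37 weeks.

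Three other statements bear on the row. The Introduction says that these women "receive an Individualized Prematurity Prevention Plan (IP3) to reduce their risk of recurrent PTB". The primary objective is to learn whether the programme is "feasible prior to a larger trial focused on determining efficacy". Under Outcome Measures, "Baseline demographics will include age, medical comorbidities, and pregnancy history", and SAP Table 1 reports "Number of Prior Preterm Births (median, IQR"), so more than one prior preterm birth per woman is foreseen.

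**The concern.** The comparison value was selected for being low and the current value was not. This is regression to the mean by design: a positive average difference is the expected result under no effect, and the table does not say so. A reader could take the figure as weeks gained, or carry it into the assumptions of the efficacy trial that is to follow. Background IP3 care could also lengthen gestation, and the row cannot separate that from the programme.

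A second worry is reproducibility. Two analysts who read *earliest* differently would report different means from the same data for women with several prior preterm births.

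**Working it through.** The plan states no expected difference, SD or power for this row, so there is no figure of its own to reproduce. The check covers the sign, the size, the wording, and what depends on the row.

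**1. Sign.** Let X1 be the qualifying prior gestation (below 37 weeks) and X2 the current one. Assume a woman's pregnancies are exchangeable and there is no programme effect. Women who are preterm both times contribute zero on average. With recurrence rate R, and mean gap D among women preterm before and term now,

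E[X2 − X1 | X1 < 37] = (1 − R) × D.

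This is positive whenever R < 1. The Introduction's 1.5 to 2 fold recurrence risk describes raised, not certain, recurrence. The same argument covers the first preterm birth in time. The lowest gestation can only be equal to that or smaller, so it gives a mean at least as large.

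**2. Size (assumptions only).** The documents give no gestational-age distribution and no within-woman correlation ρ. Two sets of assumptions, each with one prior birth:

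- *Normal gestations*, mean/SD 39/1.8, 38.5/2.0, 38.5/2.5 and 38/3.0 weeks. The mean difference is (1 − ρ) × SD × φ(a)/Φ(a), with a = (37 − mean)/SD.
  - For 39/1.8: a = −1.111 and φ/Φ = 0.2152/0.1333 = 1.615. This gives 0.8 × 1.8 × 1.615 = 2.33 weeks at ρ = 0.2, and 0.4 × 1.8 × 1.615 = 1.16 at ρ = 0.6.
  - Across all four pairs and ρ from 0.2 to 0.6: +1.06 to +2.45 weeks.
- *Left-skewed gestations*, simulated, with an assumed preterm rate of 10% or 14% and 6%, 16% and 30% of preterm births before 28, 32 and 34 weeks.

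| Preterm rate | ρ | Recurrence relative to the overall rate | Mean difference (SD), weeks |
|---|---|---|---|
| 10% | 0.2 | 1.71 | +4.14 (4.07) |
| 10% | 0.3 | 2.16 | +3.72 (4.12) |
| 14% | 0.2 | 1.56 | +3.92 (4.20) |
| 14% | 0.3 | 1.90 | +3.50 (4.27) |

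The skewed ranges lie wholly above the normal ones, so neither set is a usable estimate. The normal models imply preterm rates of 13% to 37% and put at most about 6% of preterm births before 32 weeks. At ρ = 0.6 they imply recurrence 2.8 to 4.9 times that of women without a preterm history, which sits badly with the protocol's 1.5 to 2 fold. In the skewed model the mean stays positive throughout, from +4.9 weeks at ρ = 0 to +0.6 at ρ = 0.9 (both at the 10% rate).

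With the 32 women at intake in SAP Table 6, the standard error at the first table line is 4.07/√32 = 0.72, so the no-effect mean lies 4.14/0.72 = 5.8 standard errors above zero. At the last line it is 3.50/(4.27/√32) = 4.6. Under these assumptions a positive sample mean is nearly certain.

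**3. Meaning of *earliest*.** With one prior preterm birth the two readings are identical. With two, the lowest-gestation reading is larger by 0.35 to 0.90 week in the normal models (ρ 0.2 to 0.8) and by 1.0 to 1.7 weeks in the skewed one (ρ 0 to 0.9). The shift in the overall mean is the share of such women times that gap. The share is not given. If it were a quarter (an assumption), the shift would be 0.25 × 0.35 = 0.09 to 0.25 × 1.7 = 0.43 week.

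**4. What depends on the row.** The protocol's outcomes are reach (primary), retention, fidelity and continued engagement. The SAP plans descriptive summaries and states no comparator, test or success limit for Table 5. Nothing in either document takes the row's value as an input.

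**The case for a change.** The strongest case for a change is that lack of a control group does not, by itself, tell a reader that the no-effect value lies above zero. That feature is peculiar to this row. The statement leaving efficacy to a later trial is in the protocol and is not attached to the table, which may be read alone. A definition and one sentence would cost almost nothing, since the prior gestational age is needed to compute the row anyway.

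The statistical part of this stands: the sign argument is right, and the wording does admit two readings. The call for a change does not follow. The harm is conditional on a misuse that neither document makes or plans. Most of the SAP is blank table shells, and cautions on interpretation ordinarily go in the report beside the result. The missing definition is the kind analysts settle sensibly: a row on length of gestation points to the lowest gestational age, *compared to* points to current minus prior, and the neighbouring row supplies weeks.

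Two extensions are weaker. Nothing in Table 5 sets the rows on delivery before 37 weeks or gestational age at delivery against the women's all-preterm history. And IP3 care is not purely a rival explanation, because the programme is meant to act partly by raising adherence to it.

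**Conclusion.** No change to the plan follows. A positive mean should be expected from eligibility alone, provided a woman's pregnancies are otherwise exchangeable and recurrence is below 100%. Its size is not determined by the documents; the one-prior-birth illustrations run from roughly 1 to 4 weeks depending on the assumed distribution and correlation. The ambiguity in *earliest* affects only women with more than one prior preterm birth, whose number is not given.

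Against this, the row is a descriptive line in a feasibility study, and no test, decision or conclusion rests on it. A footnote would leave the reported mean and SD as they are, and the natural reading already fills the definition. The point belongs in how the result is discussed: the figure is not an estimate of programme effect.
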